11.2 Data Collection and Management

The CASTOR system will be used as a central resource for data processing and management. Data transfer agreements will be in place with each site and the coordinating center to allow for data collection. CASTOR is a web application and back-end database model designed to support data capture for research studies. CaNVAS has a license with CASTOR that is housed on a password protected server and therefore afforded the same protections as other sensitive clinical systems. CASTOR was developed specifically around HIPAA-security guidelines with features such as data encryption. It provides an intuitive interface for data entry with data validation, audit trails for tracking data manipulation and

export procedures, automated export procedures for seamless data downloads to common statistical packages, including SAS and procedures for importing data from external sources. Standard operating procedures will be used to guide all data management activities, such as the naming and identification of variables, data cleaning and handling of missing data. Participating site data will be entered directly into the CASTOR database. Data entry screens will be designed to incorporate range checks and concurrent checks to minimize errors.

11.2.1 Protection Against Risks

All sites will obtain institutional review board approval for this study. Subject's risks of participating in research will be kept to a minimum with measures to protect confidentiality and planned interim analysis for safety monitoring.

Best of care will be provided to subjects in the event of toxicities associated with treatment. Subjects and, as applicable, parents/guardian/LAR, will be provided appropriate contact number(s) for treating physicians at the clinical site in accordance with institutional IRB guidelines.

11.2.2 Drug Accountability

Adequate records of study drug receipt and disposition will be maintained by each study site the investigational drug pharmacy. Records of receipts, investigational drug orders, dispensing records, and disposition forms will be examined during the course of the study. The purpose of these records is to ensure regulatory authorities that the investigational new drug will not be distributed to any person who is not a study subject under the terms and conditions set forth in this protocol. The study medication is to be prescribed by the Investigator or designee and may not be used for any purpose other than that described in this protocol. Supplies returned by subjects will be destroyed once returned quantities are documented. Unused supplies that expire during the study as well as those that are unused or partially used at study completion will be destroyed according to site specific SOPs.

11.3 Confidentiality

All data and records generated during this study will be kept confidential in accordance with Institutional policies and HIPAA on subject privacy and that the Investigator and other site personnel will not use such data and records for any purpose other than conducting the study.

No identifiable data will be used for future study without first obtaining IRB approval. The investigator will obtain a data use agreement between the provider (the PI) of the data and any recipient researchers (including others at CHOP) before sharing a of any Protected Health Information (PHI).

Electronic documentation will be username and password encrypted.

11.4 Regulatory and Ethical Considerations

11.4.1 Data and Safety Monitoring Plan

- Principal Investigator

The PI will have responsibility for monitoring the overall safety during the study and they or a designated appropriately clinically trained member of the study team will personally be at all of the study visits. In addition, the study coordinator will be involved in all studies and will also monitor for safety. All adverse events will be reported to the IRB in a timely fashion in compliance with all applicable regulations.

- Data Safety Monitoring Board (DSMB): The DSMB will be made up of representatives who are independent of the study sponsor and investigators.

The investigators place the highest priority on ensuring the safety of subjects participating in clinical trials. Every interventional trial conducted through CaNVAS includes a plan for safety and data monitoring.

This study will be reviewed by the CHOP Data and Safety Monitoring Board (CHOP DSMB). A summary of the CHOP DSMB activities are as follows:

- Review the clinical trial for data integrity and safety
- Review all unexpected grade 3, and all grade 4, and 5 adverse events, as well as any others requiring expedited reporting as defined in this protocol. (Grades 4 & 5 events must be reported to the DSMB within 5 calendar days of study staff's knowledge.)
- Review all DSM reports
- Submit a summary of any recommendations related to study conduct
- Terminate the study if deemed unsafe for subjects

A copy of the CHOP Data and Safety Monitoring Plan and membership roster will be maintained in the study research file and updated as membership changes. The board will review reports from the study PI twice annually (or more frequently if needed) and provide recommendations on trial continuation, suspension or termination as necessary.

Any available DSMB letters will be submitted to the IRB of record as required.

11.4.2 Audits

Auditing is essential to ensure that research conducted is of the highest quality and meets regulatory agency standards.

In accordance with ICH GCP and the audit plan, Regulatory authorities, the IRB, and/or sponsor may request access to all source documents, data capture records, and other study documentation for audit or inspection. Direct access to these documents must be guaranteed by the investigator, who must provide support at all times for these activities including;

review of subject and study related records, and compliance with protocol requirements as well as ICH GCP and applicable regulatory policies.

The key sponsor contact, monitors, auditors or regulatory inspectors are responsible for verifying source documents and records assuring that subject confidentiality is respected.

The monitor is responsible for source document verification of case report forms (CRF) data at regular intervals during the study. Protocol adherence, accuracy and consistency of study conduct and data collection with respect to local regulations will be confirmed.

By signing the investigator agreement, the investigator agrees to cooperate with the monitor to address and resolve issues identified during monitoring visits.

All data will be collected in an electronic CRF system. All entries must be completed in English. Concomitant medications and AEs will be coded. For further details surrounding the completion of CRFs, please refer to the CRF completion guidelines.

11.5 Risk Assessment

Vascular anomalies caused by Rasopathy pathways are serious conditions with no approved pharmacological treatment targeting the underlying causes of the disease. Current therapy includes lymphatic interventions, surgical procedures, and vascular occlusive procedures which mainly address symptoms and complications of the disease. There is a high unmet medical need for an effective systemic treatment that will treat the underlying cause of the disease. These patients are high risk secondary to significant morbidity of their disease and have no other medical options.

The main risks to this study are from trametinib administration. In the pediatric population, no serious suspected adverse reaction was considered expected for reporting purposes in trametinib monotherapy.

For dual therapy, the most common adverse events experienced in the trials to date as listed in the Trametinib Investigator's Brochure Edition 16 are diarrhea, nausea/vomiting, pneumonitis, rash, eye and cardiac disorders.

11.6 Potential Benefits of Trial Participation

Trametinib is considered to be a promising treatment option for pediatric and adult subjects with confirmed vascular anomalies caused by Rasopathy. Treatment with trametinib related to variants in Vascular anomalies caused by Rasopathies may provide clinical benefit compared to available treatment options. The participants enrolled in this study are planned to receive trametinib as active treatment for their disease. Based on published clinical data¹³⁻¹⁵, treatment with trametinib is expected to be tolerated with a manageable safety profile

11.6.1 Risk-Benefit Assessment

The low frequency and generally mild severity of AEs with trametinib treatment suggest good tolerability and an acceptable and manageable safety profile in pediatric and adult subjects. This represents an acceptable risk benefit assessment where the benefits of treatment outweigh the risks. These patients are high risk secondary to significant morbidity of their disease and have no other medical options.

11.7 Recruitment Strategy

Subjects will be recruited primarily through the CaNVAS member institutions with consideration given to outside provider referrals. Subjects with complex lymphatic anomalies and diminished quality of life due to condition with suspected or known Ras-pathway variants will be referred by their primary vascular anomalist, geneticist, or provider to the CaNVAS member institution. Recruitment will also include listing through clinicaltrials.gov for subjects cared for outside of the member network and at CaNVAS member sites as documented in the protocol.

There is no concern for ability to recruit this subject population given current and ongoing trends in requests for treatment of subjects with trametinib.

11.8 Informed Consent/Assent and HIPAA Authorization

Informed consent is a process that is initiated prior to the individual's agreeing to participate in the study and continues throughout the individual's study participation. Extensive discussion of risks and possible benefits of this therapy will be provided to the subjects and their families. Consent forms describing in detail the study interventions/products, study procedures and risks are given to the subject and written documentation of informed consent is required prior to starting intervention/administering study product.

Consent forms will be IRB-approved and the subject (and parent/guardian/LAR if necessary) will be asked to read and review the document. Upon reviewing the document, the investigator will explain the research study to the subject or parent/guardian/LAR and answer any questions that may arise. In accordance with 46 CR 46.111, the subject will sign and date the informed consent document prior to any procedures being done specifically for the study.

A witness should only sign when required, institutional IRB policy. If a witness signs the document when not required, the study staff should document in the legal medical record (or note to file) the relationship to the subject and why a witness signed. (i.e., "Although not required, the subject's spouse was present during the consenting process and signed as the witness." Or "Although not required, hospital staff was present for consenting process and signed as a witness.")

The subjects will have the opportunity to discuss the study with their surrogates or think about it prior to agreeing to participate. The subjects may withdraw consent at any time throughout the course of the trial.

A copy of the informed consent document will be given to the subjects for their records. The rights and welfare of the subjects will be protected by emphasizing to them that the quality of their medical care will not be adversely affected if they decline to participate in this study. If there are changes to the consent form, all revisions will be reviewed with study subject at the next appropriate opportunity. Subjects that require re-consenting will be defined in the IRB approved amendment submission. The process for obtaining informed consent will again be performed. Study subjects will not be re-consented for continuing reviews. The protocol will follow the institutional IRB's policy for subjects who demonstrate limited English proficiency or limited literacy.

After the subject's visit in which the consent is signed, it is documented in the clinic chart that the consent has been signed and that all questions have been answered to the subject's satisfaction after adequate time for review of the consent. It is also documented that a copy of the consent is given to the subject. The original consent is kept with the subject's study file, and a copy of the signed consent is sent to the Medical Records Office to be scanned into the legal medical record. A copy will also be given to the subject.

11.8.1 Waiver of Consent

Waiver of consent is not requested.

45 CFR 46.116(d) An IRB may approve a consent procedure which does not include, or which alters, some or all of the elements of informed consent set forth in this section, or waive the requirements to obtain informed consent provided the IRB finds and documents that:

- (1) the research involves no more than minimal risk to the subjects;
- (2) the waiver or alteration will not adversely affect the rights and welfare of the subjects;
- (3) the research could not practicably be carried out without the waiver or alteration; and
- (4) whenever appropriate, the subjects will be provided with additional pertinent information after participation.

11.9 Payment to Subjects/Families

Reimbursement is not provided as part of this protocol.

12 REPORTING OF PROTOCOL VIOLATIONS/DEVIATIONS AND UNANTICIPATED PROBLEMS

Any protocol violations, deviations, or unanticipated problems should be documented and reported according to the coordinating center's Manual of Operations. See the Manual for more detailed instructions.

In addition, each participating site should report protocol deviations/violations or unanticipated problems according to their site's policies, procedures and applicable regulations.

13 COORDINATING CENTER RESPONSIBILITIES:

13.1 SAE/SAE Reporting

All SAEs, regardless of attribution or expectedness, must be reported using a FDA MedWatch 3500a Form. For participating sites, this form must be submitted to the coordinating center within 24 hours of learning of the event. Participating sites are required to notify their local IRBs according to institutional reporting policies.

MedWatch 3500a Reporting Guidelines: In addition to completing appropriate subject demographic and suspect medication information, the report should include the following information within the Event Description (section 5) of the MedWatch 3500a form:

- Treatment regimen (dosing frequency, combination therapy)
- Protocol description (and number, if assigned)
- Description of event, severity, treatment, and outcome, if known
- Supportive laboratory results and diagnostics
- Investigator's assessment of the relationship of the adverse event to each investigational product and suspect medication

Follow up information to a safety report should be submitted as soon as the relevant information is available. Additional information may be added to a previously submitted report by any of the following methods:

- Adding to the original MedWatch 3500a report and submitting it as follow-up
- Adding supplemental summary information and submitting it as follow-up with the original MedWatch 3500a form
- Summarizing new information and faxing it with a cover letter including subject identifiers (i.e. D.O.B., initial, subject number), protocol description and number, if assigned, suspect drug, brief adverse event description, and notation that additional or follow-up information is being submitted (The subject identifiers are important so that the new information is added to the correct initial report.)

13.2 SAE reporting in the Follow Up Period

In the event that during the 1-year follow up period the Investigator identifies what is believed to be a new (unexpected) long-term risk or short-term risk (in the event the subject continued therapy on study drug) attributable to the study drug, this SAE must be reported to the Sponsor and to the site's IRB consistent with any Unanticipated Problem reporting policy, as this would be a new risk directly related to any subject that might be participating in the research.

13.3 Sponsor Responsibilities to be performed by the Coordinating Center:

To ensure subject safety, every SAE, regardless of causality, occurring after the subject has provided informed consent and until 30 days after the last study visit must be reported to Novartis Patient Safety ([contact]) immediately, without undue delay, but under no circumstances later than within 24 hours of obtaining knowledge of the events.

All follow-up information for the SAE including information on complications, progression of the initial SAE and recurrent episodes must be reported as follow-up to the original episode immediately, without undue delay, but under no circumstances later than within 24 hours of the Investigator receiving the follow-up information.

Any SAEs experienced after the 30-day period should only be reported to Novartis Safety if the Investigator suspects a causal relationship to study treatment.

To ensure subject safety, each pregnancy occurring after signing the informed consent must be reported to Novartis Patient Safety ([contact]) within 24 hours of learning of its occurrence. The pregnancy should be followed up to determine outcome, including spontaneous or voluntary termination, details of the birth, and the presence or absence of any birth defects, congenital abnormalities, or maternal and/or newborn complications.

13.3.1 Unexpected Fatal or Life-Threatening Suspected Adverse Reaction Reports

Notify the FDA as soon as possible but no later than 7 calendar days after the sponsor's initial receipt of the information. Either the sponsor or the investigator can make the determination of life-threatening. (Food and Drug Administration: Fax: [name])

13.3.2 Unexpected, Serious Suspected Adverse Reactions

Any suspected adverse reaction that is both serious and unexpected, per 21 CFR 312.32(c)(1)(i), **only if there is evidence to suggest a causal relationship between the drug and the adverse event**, must be reported to the FDA as soon as possible but no later than 15 calendar days after the sponsor determines the information qualifies for reporting. (Food and Drug Administration: Fax: [name]) The following must be reported:

- a. Single Occurrence – event is uncommon and known to be strongly associated with drug exposure (e.g., angioedema, hepatic injury, Stevens-Johnson Syndrome). See SOP Form 32-1.3-001 Adverse Event Reporting for the Sponsor: Single Occurrence.
- b. Multiple Occurrences – event occurs one or more times and is not commonly associated with drug exposure but is otherwise uncommon in the population exposed to the drug (e.g., tendon rupture).
- c. Aggregate Analysis of Specific Events Observed in the Clinical Trial – analysis of events, e.g., known consequences of the underlying disease or condition under investigation or other events that commonly occur in the study population independent of drug therapy, that indicates those events occur more frequently in the drug treatment group than in a concurrent or historical control group.

13.3.3 Serious Adverse Event Reporting Procedures to the CHOP IRB

The Sponsor will report any unexpected life-threatening event or death (Grade 4 or 5) adverse event to the CHOP IRB and within 24 hours after the Sponsor is made aware of the event.

Unexpected Grade 3 adverse events at least possibly attributable to the research will be reported to the CHOP IRB only at the time of the annual progress report.

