10.7 Definition of a Serious Adverse Event (SAE)

An SAE is any adverse drug experience occurring at any dose that results in any of the following outcomes:

- death,
- a life-threatening event (at risk of death at the time of the event),
- requires inpatient hospitalization or prolongation of existing hospitalization,
- a persistent or significant disability/incapacity, or
- a congenital anomaly/birth defect in the offspring of a subject.

Important medical events that may not result in death, be life-threatening, or require hospitalization may be considered a serious adverse drug event when, based upon appropriate medical judgment, they may jeopardize the subject and may require medical or surgical intervention to prevent one of the outcomes listed in this definition.

A distinction should be drawn between serious and severe AEs. A severe AE is a major event of its type. A severe AE does not necessarily need to be considered serious. For example, nausea which persists for several hours may be considered severe nausea, but would not be an SAE. On the other hand, a stroke that results in only a limited degree of disability may be considered a mild stroke, but would be an SAE.

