10.11 IRB/IEC Notification of SAEs and Other Unanticipated Problems

The Investigator will promptly notify the IRB of record of all on-site unanticipated, serious Adverse Events that are related to the research activity. Other unanticipated problems related to the research involving risk to subjects or others will also be reported promptly. Written

reports will be filed with the IRB of record and in accordance with the timeline below. External SAEs that are both unexpected and related to the study intervention will be reported promptly after the investigator receives the report.

Type of Unanticipated Problem	Initial Notification (Phone, Email, Fax)	Written Report
Internal (on-site) SAEs Death or Life Threatening	24 hours	Within 2 business days
Internal (on-site) SAEs All other SAEs	7 days	Within 7 business days
Unanticipated Problems Related to Research	7 days	Within 7 business days
All other AEs	N/A	Brief Summary of important AEs may be reported at time of continuing review

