11 STUDY ADMINISTRATION

11.1 IRB Approval

The Children's Hospital of Philadelphia (CHOP) Institutional Review Board (IRB) will serve as the reviewing IRB for this multi-center study. All participating sites have agreed to adhere to the single IRB (sIRB) Policy (<https://grants.nih.gov/grants/guide/notice-files/NOT-OD-16-094.html>) and to rely on CHOP as the sIRB.

The CHOP IRB will serve as a Privacy Board to fulfill the requirements of the Health Insurance Portability and Accountability Act (HIPAA) Privacy Rule (45 CFR 164.512(i)) for use or disclosure of protected health information for research purposes. The CHOP IRB has extensive experience with providing IRB oversight for external institutions and complies with the registration requirements for both the Office for Human Research Protections (OHRP) and the U.S. Food and Drug Administration (FDA) (IRB00000316 and IRB00000317). Prior to initiating the study, all participating sites will sign an authorization/reliance agreement that will clarify the roles and responsibilities of the sIRB and participating sites.

When the CHOP IRB serves as the reviewing IRB for other sites, it will need information from each relying institution about local context, consent form requirements (i.e. injury compensation language), applicable state/local laws and any local conflict of interest determinations. The CHOP IRB will provide approval notices and approved informed consent documents customized with the site Principal Investigator name, contact information and any other site-specific wording (i.e. injury compensation, HIPAA) for each relying institution.

As the sIRB, the CHOP IRB will communicate with the overall Principal Investigator through eIRB, which CHOP investigators also use for all other IRB submissions at CHOP. Communication with relying sites and their Principal Investigators will occur through the same system. This avoids the need to have the overall Principal Investigator collect the information from all of the relying sites and submit them to the CHOP IRB. eIRB provides the ability for Principal Investigators from each relying institution, after a simple registration process, to log in and provide site-specific documents and information (i.e. annual reports, site-specific recruitment materials) to the CHOP IRB. The CHOP IRB, in turn, will post site-specific packages (i.e. approval letters, stamped consent forms) for the use of the relying site Principal Investigators.

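### Sections 13.3.3 and 10.11 of the protocol give an unexpected, related, serious Grade 3 event two incompatible deadlines for reaching the same IRB

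*Protocol*

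**What the plan says.** Four places in the protocol govern when the IRB hears of an adverse event.

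- **Section 13.3.3**, titled "Serious Adverse Event Reporting Procedures to the CHOP IRB", has two rules. The sponsor reports unexpected life-threatening or fatal (Grade 4 or 5) events within 24 hours. Unexpected Grade 3 events with at least a possible link to the research "will be reported to the CHOP IRB only at the time of the annual progress report".
- **Section 10.11**: "The Investigator will promptly notify the IRB of record of all on-site unanticipated, serious Adverse Events that are related to the research activity". Its table gives on-site SAEs other than deaths and life-threatening events 7 days for initial notification, with the written report due "Within 7 business days".
- **Section 10.6** sends unanticipated problems, including SAEs, to the IRB of record on that board's own timelines. It leaves to continuing review only notable events that are not serious.
- **Section 11.4.1**: "All adverse events will be reported to the IRB in a timely fashion".

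Section 11.1 shows that these rules address one board. The CHOP IRB "will serve as the reviewing IRB for this multi-center study", and all sites have agreed "to rely on CHOP as the sIRB".

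**The concern.** Section 13.3.3 sorts events by grade, while section 10.11 sorts them by seriousness. The two sortings overlap. An event can be Grade 3, serious, unexpected and related all at once, and the protocol then gives two different dates for telling the same IRB.

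What is at stake is the IRB's own role. Under section 11.8 it approves the consent forms, and re-consent follows from an amendment that it has approved. A new serious risk that reaches the board late can delay a change to what families are told. In addition, 25 sites rely on this one board, and two conflicting instructions invite inconsistent reporting between them.

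**Working it through.** No sample size, power or error rate enters this point, so the check is a comparison of text.

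**Step 1: same board?** Yes. Section 10.11 speaks of the IRB of record and section 13.3.3 of the CHOP IRB. Section 11.1 makes them the same body.

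**Step 2: can a Grade 3 event be serious?** Yes. Section 10.7 defines seriousness by outcome, and one criterion is an event that "requires inpatient hospitalization or prolongation of existing hospitalization". It also warns that severity and seriousness differ. The protocol gives its own examples:
- Section 10.2.6.5 says a symptomatic Grade 3 fall in ejection fraction is to be reported as an SAE.
- Section 10.2.6.8 says the same of retinal pigment epithelial detachment or retinal vein occlusion diagnosed with a Grade 2 or 3 visual event.

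**Step 3: can such an event be unexpected?** Yes. Section 11.5 states that for trametinib monotherapy in children no serious suspected adverse reaction counts as expected for reporting purposes. On that statement, a child's serious, related Grade 3 event would be unexpected and fall under both rules.

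**Step 4: compare the clocks for that event.**

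| Source | Time to the IRB |
|---|---|
| 10.11 | 7 days (notice); 7 business days (written report) |
| 10.6 | the IRB's required timelines; deferral for non-serious events only |
| 11.4.1 | timely, no figure given |
| 13.3.3 | annual report only: up to about 12 months |

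The 12 months is the longest wait. If events fall evenly over the reporting year, the average wait is about 12 / 2 = 6 months.

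**Step 5: can both rules be kept?** Not as written. An annual summary could sit beside a 7-day report, but the word *only* in 13.3.3 excludes that. Section 13.3.3 is the outlier among the four.

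**Step 6: who else receives the event, and when?**
- Coordinating center: 24 hours under 13.1. Section 10.12 gives 7 business days when the event is neither fatal nor life-threatening.
- Manufacturer's safety unit: 24 hours (13.3).
- FDA: 15 calendar days, if it qualifies as a serious, unexpected suspected reaction with evidence of causality (13.3.2).
- DSMB: reviews all unexpected Grade 3 events. Its 5-day clock covers Grades 4 and 5 only. Reports come twice a year or more often, so the longest routine gap is about 12 / 2 = 6 months (11.4.1).

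**The case against.** Two readings would remove the conflict.

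*Different reporters.* Section 10.11 binds the investigator, whereas 13.3.3 sits under sponsor duties carried out by the coordinating center. The sponsor's annual summary would then leave the site's 7-day duty intact. This is plausible, but the Grade 3 sentence names no reporter, and it says that these events reach the board only once a year.

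*Non-serious events only.* The Grade 3 sentence speaks of adverse events rather than SAEs. If limited to non-serious events, it would agree with 10.6 and with the last row of the 10.11 table. That may well be the intent. The section heading, however, says serious, and no carve-out is written.

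The objection does stand on the consequence. Three other sections already call for prompt or timely reporting, so the long delay arises only if someone follows 13.3.3 in preference to them.

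A reader might infer that a new serious risk could go unreviewed for a year. The documents do not support that, because the recipients in step 6 have shorter clocks and the DSMB can terminate the study. Nor do they support the inference that the IRB would hear nothing while enrollment continues. Section 4.7.1 plans 2 years of recruitment, so an annual report would ordinarily fall within it. A count of subjects enrolled during the delay would require even accrual, a full year's wait, no site report under 10.11 and no action by any other recipient. It would be a worst case, not an estimate.

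**Conclusion.** The contradiction is real and narrow. It concerns events that are Grade 3, serious, unexpected and related. For these the protocol states both 7 days and up to about 12 months to the same IRB, and it does not say which governs. If 13.3.3 is followed, IRB receipt may be late by up to about a year, although other safety bodies would have the event sooner.

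This rests on two assumptions: that the annual progress report comes every 12 months, and that the IRB's own procedures, which 10.6 invokes and the protocol does not reproduce, do not already override 13.3.3. It is an internal contradiction in safety reporting, not a design choice, and it touches neither the endpoint nor the analysis. It should be corrected because the text is a standing instruction to 25 sites and the correction is small.

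**What to change.** Reconcile 13.3.3 with 10.6, 10.11 and 11.4.1. Limit its annual-report sentence to Grade 3 events that are not serious, and add that serious, unexpected, related Grade 3 events follow the 10.11 timelines. Leave the 24-hour rule for Grade 4–5 events as it stands. It would help to name who reports, so that the sponsor's and the investigator's duties are not read as alternatives.

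The cost is one sentence in the next amendment. It creates no report that 10.11 does not already require and changes no treatment rule.
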